4.1.4 Safety Endpoints

- Adverse events
- Serious adverse events
- Laboratory parameters and vital signs

4.1.5 Exploratory

- mTSS, Erosion Score (ES), and Joint Space Narrowing (JSN) at baseline, week 24, and week 48
- Change from baseline in mTSS, ES and JSN at week 24 and week 48
- Percent change from baseline in mTSS, ES and JSN at week 24 and week 48
- Non-progression in mTSS defined as change in 3 levels: change ≤ 0 , change ≤ 0.5 , change ≤ 3 , from baseline at week 24 and week 48
- Very Low Disease Activity (VLDA) response at week 24 and all other measured time points
- Disease Activity index for Psoriatic Arthritis (DAPSA) and change from baseline at week 24 and all other measured time points

- Health Assessment Questionnaire Disability Index (HAQ-DI) score and change from baseline at all measured time points other than week 24
- Short Form (36) Health Survey Version 2 (SF-36v2) (MCS and PCS) score and change from baseline at all measured time points other than week 24

For subjects with non-zero mNAPSI at baseline,

- mNAPSI and change from baseline at all measured time points other than week 24
- achievement of mNAPSI = 0 at all measured time points other than week 24

For subjects with non-zero Leeds Dactylitis Index (LDI) at baseline,

- LDI and change from baseline at all measured time points other than week 24
- achievement of LDI = 0 at all measured time points other than week 24

For subjects with non-zero Spondyloarthritis Research Consortium of Canada (SPARCC) enthesitis at baseline,

- SPARCC enthesitis score and change from baseline at all other measured time points other than week 24
- achievement of SPARCC score = 0 at all measured time points other than week 24

For subjects with involved body surface area (BSA) $\geq 3\%$ at baseline, $< 3\%$ at baseline, and $\geq 3\%$ but $< 10\%$ at baseline, $\geq 10\%$ at baseline:

- Static Physician Global Assessment (sPGA) categorical summary by 0,1,2,3,4,5 at all measured time points other than week 24
- sPGA continuous summary at all measured time points other than week 24
- sPGA of 0 or 1 (yes/no) at all measured time points other than week 24
- sPGA one grade improvement from baseline at all measured time points other than week 24
- sPGA two grade improvement from baseline at all measured time points other than week 24
- BSA, change and percent improvement from baseline at all measured time points other than week 24

4.2 Planned Covariates

The following covariates will be considered to assess their influence on the primary and key secondary endpoints:

- Age (≤ 65 , > 65)
- Sex (male, female)
- Race (Caucasian, non-Caucasian)
- Ethnicity (Hispanic or Latino, non-Hispanic or Latino)

- Baseline body mass index (BMI) (≤ 30 , > 30)
- Baseline weight (≤ 100 kg, > 100 kg)
- Baseline BSA ($\leq 3\%$, $> 3\%$, $3-10\%$, $\geq 10\%$)
- Prior use of non-biologic DMARD (yes, no)
- Disease duration (\leq median, $>$ median, $< =$ mean, $>$ mean)

Subgroup analyses based on these covariates will be performed for the primary and key secondary endpoints to examine any differences in drug responses.

5. Hypotheses and/or Estimations

The primary hypothesis of this study is that etanercept plus methotrexate therapy and etanercept monotherapy are more efficacious than methotrexate monotherapy as measured by the proportion of subjects with PsA achieving ACR 20 response at week 24.

The secondary hypothesis of this study is that etanercept plus methotrexate therapy and etanercept monotherapy are more efficacious than methotrexate monotherapy as measured by the proportion of subjects with PsA achieving MDA response at week 24.

6. Definitions

6.1 Basic Definitions

Actual treatment received

Actual treatment for a subject is defined as the treatment the subject is randomized. An exception would be when a subject receives a different treatment other than the randomized treatment throughout the whole course of the study period, and then the actual treatment will be defined as the actual treatment received. In this context, treatment may refer to one Investigational product (IP), or a combination of IPs.

The following scenarios are examples of how actual treatment is defined in double blinded period:

| Planned Treatment | Actual Treatment |
|-----------------------------------|---|
| Etanercept + Methotrexate | 
If subject receives all placebo doses of Etanercept and all placebo doses of Methotrexate then Actual arm = Etanercept+ Methotrexate
 
Else if subject receives at least one dose Etanercept and all placebo doses for Methotrexate then Actual arm = Etanercept + Placebo Methotrexate
 
Else If subject receives at least one dose Methotrexate and all placebo doses for Etanercept then Actual arm = Methotrexate + Placebo Etanercept
 
Else Actual arm = Etanercept + Methotrexate
 |
| Etanercept + Placebo Methotrexate | 
If subject receives all doses of placebo Etanercept and at least one dose of placebo Methotrexate then Actual arm = Etanercept +Placebo Methotrexate ,
 
Else if subject receives at least one dose Etanercept and all doses of Methotrexate then Actual arm = Etanercept + Methotrexate
 
Else Actual arm = Etanercept + Placebo Methotrexate
 |
| Methotrexate + Placebo Etanercept | 
If subject receives at least one dose placebo Etanercept and all placebo doses for Methotrexate then Actual arm = Placebo Etanercept + Methotrexate
 
Else if subject receives at least one dose Methotrexate and all doses of Etanercept then Actual arm = Etanercept + Methotrexate
 
Else Actual arm = Methotrexate + Placebo Etanercept
 |

Actual treatment received in rescue period is defined as etanercept + methotrexate.

Age

Number of years at time of enrollment as recorded on the electronic case report form.

Imputed Value

A value substituted for a missing value.

Investigational Product (IP)

Etanercept (or placebo for etanercept) and methotrexate (or placebo for methotrexate).

Last Observation Carried Forward (LOCF) Imputation

A method of imputation where missing post-baseline efficacy data will be carried forward from the last non-missing post-baseline value for that endpoint.

Rescue Therapy

It is defined as subjects whose IP admin CRF forms indicate whether a subject receives rescue IPs or not.

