7.3 Safety Analysis Set

The safety analysis set will consist of all randomized subjects who receive at least one dose of investigational product. Subjects will be analyzed according to the actual treatment received as defined in [Section 6.1](#). Analyses of safety endpoints will be based on the safety analysis set.

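### SAP 6.1's actual-treatment table contradicts the definition above it for a subject who receives the other monotherapy throughout

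*SAP*

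**What the plan says.** SAP 6.1 starts from the randomized treatment and then allows one departure: "An exception would be when a subject receives a different treatment other than the randomized treatment throughout the whole course of the study period", in which case "then the actual treatment will be defined as the actual treatment received". A table of If/Else rules for the double-blind period follows, introduced by "The following scenarios are examples of how actual treatment is defined in double blinded period". Each planned arm has its own chain of tests, and each chain closes with an unconditional Else that returns the planned arm.

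The etanercept monotherapy row has two tests before its Else. The opening one reads "If subject receives all doses of placebo Etanercept and at least one dose of placebo Methotrexate then Actual arm = Etanercept +Placebo Methotrexate". The other sends a subject with some active etanercept and only active methotrexate to the combination.

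The methotrexate monotherapy row opens with "If subject receives at least one dose placebo Etanercept and all placebo doses for Methotrexate then Actual arm = Placebo Etanercept + Methotrexate". Its second test sends a subject with some methotrexate and only active etanercept to the combination. It then closes with "Else Actual arm = Methotrexate + Placebo Etanercept".

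The combination row, by contrast, has one branch leading to each monotherapy.

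SAP 7.3 applies the definition to the safety analysis set: "Subjects will be analyzed according to the actual treatment received as defined in" Section 6.1. SAP 10.6 runs the safety analyses on that set. Protocol 10.1.2.3 also calls for safety analysis by the treatment actually received.

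**The concern.** A subject who receives another arm's treatment from start to finish is the case an actual-treatment rule exists to handle. The sentence in SAP 6.1 handles it; the table below it does so only in part. The etanercept row can return only etanercept monotherapy or the combination. The methotrexate row can return only methotrexate monotherapy or the combination. A full swap between the two monotherapies therefore has no route to the correct label.

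What is at stake is attribution of safety events. Protocol 6.2.2.2 lists raised transaminases as a typical methotrexate toxicity, and SAP 10.6.2 names AST and ALT among the analytes for shift tables by treatment group. Under the table, a subject randomized to etanercept monotherapy but given only methotrexate would have any such finding shown under etanercept monotherapy. The reverse swap would place events that occurred on etanercept under methotrexate monotherapy.

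**Working it through.** The plan gives no figure to reproduce here; the check is one of decision logic.

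**Inputs.** These are the definition and the three table rows in SAP 6.1, and the planned size of about 280 per arm in SAP 3.1. Whole course is read as the whole double-blind period, which is the period the table covers.

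**Step 1: trace every uniform pattern.** Write E for etanercept monotherapy, M for methotrexate monotherapy and E+M for the combination. Three planned arms times three received regimens gives 9 cases, of which 6 are switches.

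| Planned | Received throughout | Branch reached | Table returns | Definition requires |
|---|---|---|---|---|
| E+M | E+M | Else | E+M | E+M |
| E+M | E | second | E | E |
| E+M | M | third | M | M |
| E | E | Else | E | E |
| E | E+M | second | E+M | E+M |
| E | M | Else | **E** | **M** |
| M | M | Else | M | M |
| M | E+M | second | E+M | E+M |
| M | E | Else | **M** | **E** |

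**Step 2: the two mismatches in detail.**
- Planned E, received all placebo etanercept and all active methotrexate. The first test needs at least one placebo methotrexate dose, and there is none. The second needs at least one active etanercept dose, and there is none. Else returns E.
- Planned M, received all active etanercept and all placebo methotrexate. The first test needs at least one placebo etanercept dose, and there is none. The second needs at least one active methotrexate dose, and there is none. Else returns M.

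Agreement is 7 of 9 overall. Among the switches it is 4 of 6, with 2 of 6 contradicted.

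**Step 3: size per subject.** Suppose one misplaced subject has the event in question.
- Let the arm that wrongly holds the subject show x events in 280, where the correct figure is (x − 1)/279. The error is x/280 − (x − 1)/279 = (280 − x)/(280 × 279). It is largest at x = 1, where it equals 1/280 = 0.36 percentage points.
- Let the arm that should hold the subject show y events in 280, where the correct figure is (y + 1)/281. The error is (280 − y)/(280 × 281). It is largest at y = 0, where it equals 1/281, also 0.36 percentage points.

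**Step 4: effect of the repair.** Add to row E a branch for all placebo etanercept with all active methotrexate, returning M. Add the mirror branch to row M, returning E. Both patterns already fail the existing tests, so each branch can sit just before the Else. Mismatches fall from 2 of 9 to 0 of 9, and no other pattern changes its label.

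**The case against.** The strongest defence is that the governing sentence is right and the table is offered only as examples. SAP 7.3 points to Section 6.1 as a whole, which includes that sentence, so the plan does not lack a correct rule. This stands in part: the fault is an inconsistency between a correct definition and its table. It does not clear the table. Each row ends in a catch-all, so these two subjects are not left to the definition but are given the wrong arm.

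The practical weight is also small, and that stands. Both separately supplied products would have to be wrong for the whole period. For a subject who completes without rescue, Table 1 of the protocol schedules six dispensations of each product. Safety has no formal testing (SAP 10.1). Important protocol deviations related to dosing are tabulated (SAP 9.4), and grade 3 and 4 laboratory values are listed by subject (SAP 10.6.2), so such a case might be noticed by another route.

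A reader might infer several stronger points that the documents do not support:
- **That mixed exposure is misclassified too.** An example is a methotrexate-arm subject with no active methotrexate and all but one injection active, who stays under methotrexate. The exception covers only a different treatment for the whole course. A mixed pattern does not clearly meet it, so keeping the randomized arm is defensible. The combination row does treat similar mixtures differently, but that is a question of policy and not a breach of the definition.
- **That the programmed derivation is wrong.** The code fragments in SAP Appendix B are redacted, so this cannot be checked. The misreporting is conditional on the table being followed.
- **That every safety table is affected.** Actual treatment in the rescue period is fixed separately as the combination (SAP 6.1), and rescue events are summarized separately (SAP 10.6).
- **That the gap is certainly an oversight.** The branches in the combination row suggest so. However, the first test in the etanercept row deliberately keeps some subjects with no active etanercept in that arm, so intent cannot be settled from the text. The contradiction does not depend on intent.

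**Conclusion.** The point holds as a contradiction within SAP 6.1, limited to two patterns: a whole-course switch from etanercept monotherapy to methotrexate monotherapy, and the reverse. Its reach is the double-blind-period safety summaries by actual treatment. The primary and key secondary analyses use the randomized arm (SAP 7.1 and 10.5) and are untouched.

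The bound of about 0.36 percentage points per arm applies to each misplaced subject with the event and assumes about 280 subjects per arm. The total effect depends on how many subjects were fully swapped. The documents do not say; the number is probably very small and may be zero. The case for correcting the table is that a written rule gives the wrong arm in the very situation its definition addresses, and the repair is simple.

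**What to change.** In the SAP 6.1 table, add one branch immediately before the Else in each monotherapy row:
- Planned etanercept monotherapy: if all etanercept doses are placebo and all methotrexate doses are active, Actual arm = Methotrexate + Placebo Etanercept.
- Planned methotrexate monotherapy: if all etanercept doses are active and all methotrexate doses are placebo, Actual arm = Etanercept + Placebo Methotrexate.

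Leave the handling of mixed-exposure patterns unchanged. Looser branches triggered by a single active dose would move subjects whom the definition does not clearly take out of their randomized arm. For example, a subject in the etanercept row with only placebo injections and one active methotrexate dose would become a methotrexate subject.

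The cost is two lines of SAP text and the matching lines in the derivation program, if it follows the table. The change is best made before unblinding, so that any reassignment is not a post hoc decision.

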6.2 Study Points of Reference

Study Baseline

The last non-missing measurement for the endpoint of interest taken on or before the first dose of investigational product.

For swollen joint count and tender joint count, the baseline values are the values taken on or before the day of the first dose of investigational product, and on or after randomization date.

Study Day

The number of days from Study Day 1, inclusive, given by the following formula:

Study Day = (Date of Interest – Date of Study Day 1) + 1, for Date of Interest is on/after Study Day 1

Study Day = Date of Interest - Date of Study Day 1, for Date of Interest is before Study Day 1

Study Day 1

The first day of IP administration after randomization, if a subject is never dosed but randomized, then set study day 1 to randomization date.

6.3 Study Dates

End of Study Date

Date of the End of Study (EOS) safety follow-up phone call (for subjects who complete the study) or Early Termination (ET) visit (for subjects who withdraw from the study prematurely).

First Dose Date

The date of the first dose of IP.

Last Dose Date

The date of the last dose of IP.

Randomization Date

The date when a randomization number is assigned through the Interactive Voice/Web Response System (IVRS/IWRS).

6.4 Study Time Intervals

Double-blind Treatment Period

The period of time beginning when a subject receives their first dose of IP through the first dose of rescue treatment, or end of study if they are never rescued. In case where a

subject is randomized but never dosed, the double blind period will start on the randomization date.

Rescue Therapy Period

The period of time between the first dose of open-label rescue therapy at or after week 24 through end of study.

6.5 Calculations

Body Mass Index (BMI)

A measure utilizing both height and weight, as given by the following formula: weight (kg) / squared height (m²).

Duration of Psoriatic Arthritis

The number of years between the date of diagnosis (DXDT) and study Day 1, rounded to one decimal place, is given by formula below to calculate the duration:

| Observed portion | Missing portion | Formula to Calculate Duration |
|------------------|-----------------|---|
| Year, Month, Day | | $(DAY\ 1 - DXDT + 1)/365.25$ |
| Year, Month | Day | $[Year(DAY\ 1)-Year(DXDT)]+$ $[Month(DAY\ 1)-Month(DXDT)]/12$ *if duration equals 0, add 1 month or 1/12 years (this is to avoid a disease duration of 0) |
| Year | Month, Day | $[Year(DAY\ 1)-Year(DXDT)]$ *if duration equals 0, add 1 month or 1/12 years (this is to avoid a disease duration of 0) |

Improvement from Baseline

The arithmetic difference between the baseline value and a post-baseline value, as given by the following formulas:

For endpoints with higher scores as better clinical results,
Improvement from baseline = (Post-baseline Value – Baseline Value)

For endpoints with lower scores as better clinical results,
Improvement from baseline = (Baseline Value – Post-baseline Value)

Percent Improvement from Baseline

The improvement from baseline divided by baseline and multiplied by 100, as given by the following formula:

$$(\text{Improvement from Baseline} / \text{Baseline}) * 100$$

Note: If improvement from baseline is 0, the percent improvement from baseline will be set to 0 regardless of the baseline value. If the baseline value is 0, substitute 1 in the denominator for the percent improvement from baseline calculation.

6.6 Study Endpoints

ACR 20

A positive ACR 20 response is defined as at least 20% improvement from baseline in both tender/painful (68 joints) and swollen joint counts (66 joints), and at least 20% improvement in at least 3 of the following criteria: physician global assessment of arthritis disease activity (PhGA, 0-100 visual analog scale), patient global assessment of arthritis disease activity (PtGA, 0-100 visual analog scale), patient global assessment of joint pain (0-100 visual analog scale), functional disability (HAQ-DI), and acute phase reactant [C-reactive protein (CRP)].

Details of the scoring algorithm are described in [Appendix A](#).

ACR 50

A positive ACR 50 response is defined by using the definition of ACR 20 response described above but requiring at least 50% improvement.

ACR 70

A positive ACR 70 response is defined by using the definition of ACR 20 response described above but requiring at least 70% improvement.

Adverse Event

In addition to the International Conference on Harmonisation (ICH) Guidance definition, an adverse event also includes any occurrence or worsening of a pre-existing medical condition.

Body Surface Area (BSA)

A numerical score (0% to 100%) that measures psoriasis involvement by the proportion of the subject's total body surface area involved with psoriasis.

Clinical Disease Activity Index (CDAI)

A composite score that is based on the number of tender and swollen joints using a 28-joint count, PhGA (0-10 visual analog scale), and PtGA (0-10 visual analog scale). A higher score represents worse disease.

Details of the scoring algorithm are described in [Appendix A](#).

C-Reactive Protein (CRP)

A specific measure of inflammatory activity measured in mg/dL.

Disease Activity Score (DAS28-CRP)

A composite index that was designed to measure disease activity in subjects using the number of tender and swollen joints based upon a 28-joint count, CRP in mg/L, and a 100 mm visual analog scale measuring the subject's general health. A higher score represents worse disease.

Details of the scoring algorithm are described in [Appendix A](#).

Disease Activity index for Psoriatic Arthritis (DAPSA)

This index is a composite measure, which comprises swollen and tender joint counts, patient global and pain assessment and an acute phase reactant. Details of the scoring algorithm are described in [Appendix A](#).

Disability Index of the Health Assessment Questionnaire (HAQ-DI)

The HAQ-DI assesses the subject's physical function or disability. The questionnaire asks about the degree of difficulty a person has in accomplishing tasks in 8 functional areas (dressing, arising, eating, walking, hygiene, reaching, gripping, and usual activities). Responses in each functional area are scored from 0 indicating no difficulty to 3 indicating inability to perform a task in that area.

Details of the scoring algorithm are described in [Appendix A](#).

Leeds Dactylitis Index (LDI)

The Leeds Dactylitis Index (LDI) quantitatively measures dactylitis using the circumference of involved digits and circumference of control digits (either contralateral digit, ie, digits on opposite hand or foot, or digit in standard reference table), and tenderness of involved digits. The ratio of affected digit circumference to control digit circumference is multiplied by a tenderness score if ratio difference is greater than 10%. The results from each involved digit are then summed to provide the final LDI. A higher LDI is associated with worse dactylitis.

Details of the scoring algorithm are described in [Appendix A](#).

Leeds Enthesitis Index

The Leeds enthesitis index assesses enthesitis at 6 sites for palpitation with a resultant score of 0 to 6. Tenderness at each site is quantified on a dichotomous basis (0 = non-tender, 1 = tender). Entheses assessed are lateral epicondyles (left and right), medial femoral condyles (left and right), and achilles tendon insertions (left and right). A higher count represents greater enthesitis burden.

Details of the scoring algorithm are described in [Appendix A](#).

Medical Outcomes Health Survey Short Form 36 Items Version 2 (SF-36 v2)

The SF-36 v2 is a 36-item instrument that measures general health status and will be scored using the Quality Metric Health Outcomes Scoring Software. It includes 8 multi-item scales, each of which assesses one of the following 8 health concepts over the previous month: 1) limitations in physical activities because of health problems; 2) limitations in social activities because of physical or emotional problems; 3) limitations in usual role activities because of physical health problems; 4) bodily pain; 5) general mental health (psychological distress and well-being); 6) limitations in usual role activities because of emotional problems; 7) vitality (energy and fatigue); and 8) general health perceptions. SF-36 v2 includes the Physical Component Summary and Mental Component Summary measures. A higher score represents less disability.

Minimal Disease Activity (MDA)

A measure of low disease activity specific for PsA that incorporates measures of joint and enthesal inflammation, skin disease, PROs and functional disability to assess the subject's disease activity. Subjects are classified as achieving MDA if they fulfill 5 of the following 7 outcome measures:

- Tender joint count (0-68) ≤ 1
- Swollen joint count (0-66) ≤ 1
- Body Surface Area (BSA) ≤ 3
- Patient global assessment of joint pain (0-100) ≤ 15
- Patient global assessment of disease activity VAS (0-100) ≤ 20
- HAQ-DI (0-3) ≤ 0.5
- SPARCC enthesitis index ≤ 1

Details of the scoring algorithm are described in [Appendix A](#).

Modified Nail Psoriasis Severity Index (mNAPSI)

The modified NAPSI scale is an objective, numeric, and reproducible grading system for nail psoriasis that incorporates the following 7 clinical features:

- pitting (scores 0-3, depending on the number of pits)
- nail plate crumbling (scores 0-3, depending on the % of nail involvement)
- onycholysis and oil drop dyschromia (scores 0-3, depending on the % of nail involvement)
- leukonychia (0 = absent, 1 = present)
- red spots in lunula (0 = absent, 1 = present)

- nail bed hyperkeratosis (0 = absent, 1 = present)
- splinter hemorrhages (0 = absent, 1 = present)

In randomized subjects with fingernails involved with psoriasis, each fingernail will be scored at baseline to determine the worst fingernail (ie, the fingernail with the highest mNAPSI score). This fingernail will be followed for the remainder of the study. If multiple fingernails have the same worst score, only one target fingernail will be followed. Scores will range from 0-13 where higher scores represent worse nail disease.

Details of the scoring algorithm re described in [Appendix A](#)

Patient Global Assessment of Joint Pain (PtGAJP)

An assessment of the severity of the subject's joint pain (0=no pain at all, 100 = worst pain imaginable) completed by the patient using a visual analog scale (VAS).

Patient Global Assessment of Disease Activity (PtGA)

A global assessment of the subject's arthritis (0 = no arthritis activity at all, 100 = worst arthritis activity imaginable) completed by the patient using a visual analog scale (VAS).

Physician Global Assessment of Disease Activity (PhGA)

A global assessment of the subject's arthritis (0 = no activity at all, 100 = worst activity imaginable) completed by the physician using a visual analog scale (VAS).

Psoriatic Arthritis Disease Activity Score (PASDAS)

A score of disease activity consisting of the following domains: physician and patient global assessment of disease activity (0-100 visual analog scale), peripheral joint counts based upon 68/66 joints, tender dactylitis count, Leeds enthesitis index, CRP in mg/L and SF-36 v2 physical component summary.

Details of the scoring algorithm are described in [Appendix A](#).

Simplified Disease Activity Index (SDAI)

A composite score that is based on the number of tender and swollen joints using a 28-joint count, PhGA (0-10 visual analog scale), PtGA (0-10 visual analog scale), and CRP in mg/dL. A higher score represents worse disease.

Details of the scoring algorithm are described in [Appendix A](#).

Spondyloarthritis Research Consortium of Canada (SPARCC) Enthesitis Index

The SPARCC enthesitis index assesses enthesitis at 18 sites for palpation with a resultant score of 0 to 16. Tenderness at each site is quantified on a dichotomous basis (0 = non-tender, 1 = tender). Entheses assessed are medial epicondyle (left and right),

lateral epicondyle (left and right), supraspinatus insertion into greater tuberosity of humerus (left and right), greater trochanter (left and right), quadriceps insertion into superior border of patella (left and right), patellar ligament insertion into inferior pole of patella or tibial tubercle (left and right), Achilles tendon insertion into calcaneum (left and right), plantar fascia insertion into calcaneum (left and right). A higher count represents greater enthesitis burden.

Details of the scoring algorithm are described in [Appendix A](#).

Static Physician Global Assessment of Psoriasis (sPGA)

The static Physician Global Assessment of psoriasis (sPGA) evaluates the physician's global assessment of the subject's psoriasis based on severity of induration, scaling, and erythema. The sPGA is assessed on a scale of 0 (clear) to 5 (severe).

Swollen Joint Count

A score that assesses the presence or absence of swelling in 66 joints. Details of the scoring algorithm are described in [Appendix A](#).

Tender Joint Count

A score that assesses the presence or absence of tenderness in 68 joints. Details of the scoring algorithm are described in [Appendix A](#).

Treatment Emergent AE

A treatment emergent AE is defined as an event that occurs on or after the initiation of the IP and prior to the EOS date (ie, 30 days after last dose of IP). It is determined by the pre-treatment flag (ie, AE.AEPRETRT NE 'Y') on the Events CRF with a start date up to 30 days after the end of investigational product or the End of Study date, whichever is earlier.

Van der Heijde Modified Total Sharp Score (mTSS)

A method for assessing erosions and joint space narrowing of the hands and feet based on the Sharp-van der Heijde method in rheumatoid arthritis. The method is adapted for evaluation of PsA by including the distal interphalangeal joints of the hand and scoring not only for erosions and joint space narrowing but also for subluxation, ankylosis, gross osteolysis, and pencil in cup phenomena. The maximum possible total score is 528.

A higher score represents worse destruction. Details of the scoring algorithm are described in [Appendix A](#).

Very Low Disease Activity (VLDA)

A measure of very low disease activity specific for PsA that incorporates measures of joint and enthesal inflammation, skin disease, PROs and functional disability to assess the subject's disease activity. Subjects are classified as achieving VLDA if they fulfill all the following 7 outcome measures:

- Tender joint count (0-68) ≤ 1
- Swollen joint count (0-66) ≤ 1
- Body Surface Area (BSA) ≤ 3
- Patient pain VAS (0-100) ≤ 15
- Patient global disease activity VAS (0-100) ≤ 20
- HAQ (0-3) ≤ 0.5
- Tender enthesal points ≤ 1

Details of the scoring algorithm are described in [Appendix A](#).

7. Analysis Subsets

